10.3.5. Medical Monitor and GCSP Physician Actions

- Medical Monitor must notify PI of VSLC's rechallenge (or restart) decision and recommended dosing regimen in writing and Medical Monitor must record note in study files.
- The Safety Review Team must record rechallenge (or restart) outcomes and the GCSP Physician must send these to the VSLC (see template below).
- All severe reactions (rechallenge associated with bilirubin >2xULN or jaundice, or INR ≥ 1.5), SAEs or fatalities which occur following a drug rechallenge (or restart) must be immediately reported to Line Management including, VSLC

Chair, VP Global Medical Strategy and EU Qualified Person for Pharmacovigilance.

10.3.6. PI Actions:

- The PI must obtain Ethics Committee or Institutional Review Board approval of drug rechallenge or restart, as required.
- If VSLC approves drug rechallenge or restart, the patient must sign a new informed consent containing a clear description of possible benefits and risks of drug administration including recurrent, more severe liver injury or possible death.
- ***Targeted drug rechallenge or drug restart consent form must be used.***
- The patient's informed consent must be recorded in the study chart, and the drug administered at agreed dose, as communicated by Medical Monitor.
- Liver chemistries must be followed ***twice weekly for 'rechallenge' cases and once weekly for 'restart' cases*** for a minimum of one month and thereafter for as long as clinically indicated following drug re-initiation. If participant exhibits protocol-defined liver chemistry elevations, IP should be discontinued as protocol specified.
- Medical Monitor and the Ethics Committee or Institutional Review Board must be informed of the patient's outcome following drug rechallenge or restart.

Drug Rechallenge or Drug Restart Outcomes Table Template

To be completed/updated and provided to VSLC with each event recorded across studies and indications

Drug Rechallenge/Restart Outcomes Table – Update with each event

Protocol#	Participant#	Rechallenge or Restart?	Safety outcome*	Drug benefit

Rechallenge/restart safety outcomes:

0 = no liver chemistry elevation

1 = recurrent liver chemistry elevation not meeting participant stopping criteria

2 = recurrent liver chemistry elevation meeting participant stopping criteria

3 = serious adverse event

4 = fatality

10.4. Appendix 4: CDC Classification for HIV-1 Infection (2014)

Note that the CD4+ T-lymphocyte count takes precedence over the CD4+ T-lymphocyte percentage in HIV infection stages 1, 2, and 3. The CD4+ T-lymphocyte should only be considered if the count is missing.

HIV infection, stage 0

Indicates early HIV infection, inferred from a negative or indeterminate HIV test result within 180 days of a positive result. The criteria for stage 0 supersede and are independent of criteria used for other stages.

HIV infection, stage 1

- Laboratory confirmation of HIV infection with no AIDS-defining condition, and
 - CD4+ T-lymphocyte count of ≥ 500 cells/ μ L, or
 - CD4+ T-lymphocyte percentage of total lymphocytes of $\geq 26\%$.

HIV infection, stage 2

- Laboratory confirmation of HIV infection with no AIDS-defining condition, and
 - CD4+ T-lymphocyte count of 200 to 499 cells/ μ L, or
 - CD4+ T-lymphocyte percentage of total lymphocytes of 14% to 25%.

HIV infection, stage 3 (AIDS)

- Laboratory confirmation of HIV infection, and
 - CD4+ T-lymphocyte count of < 200 cells/ μ L, or
 - CD4+ T-lymphocyte percentage of total lymphocytes of $< 14\%$, or
 - Documentation of an AIDS-defining condition (see below).

Documentation of an AIDS-defining condition supersedes a CD4+ T-lymphocyte count of > 200 cells/ μ L and a CD4+ T-lymphocyte percentage of total lymphocytes of $> 14\%$.

HIV infection, stage unknown

- Laboratory confirmation of HIV infection, and
 - No information on CD4+ T-lymphocyte count or percentage, and
 - No information on presence of AIDS-defining conditions.

Stage-3-defining opportunistic illnesses in HIV infection

- Candidiasis of bronchi, trachea, or lungs
- Candidiasis of oesophagus
- Cervical cancer, invasive

- Coccidioidomycosis, disseminated or extrapulmonary
- Cryptococcosis, extrapulmonary
- Cryptosporidiosis, chronic intestinal (>1 month's duration)
- Cytomegalovirus disease (other than liver, spleen, or nodes), onset at age >1 month
- Cytomegalovirus retinitis (with loss of vision)
- Encephalopathy, HIV-related
- Herpes simplex: chronic ulcers (>1 month's duration) or bronchitis, pneumonitis, or oesophagitis (onset at age >1 month)
- Histoplasmosis, disseminated or extrapulmonary
- Isosporiasis, chronic intestinal (>1 month's duration)
- Kaposi's sarcoma
- Lymphoma, Burkitt's (or equivalent term)
- Lymphoma, immunoblastic (or equivalent term)
- Lymphoma, primary, of brain
- Mycobacterium avium complex or Mycobacterium kansasii, disseminated or extrapulmonary
- Mycobacterium tuberculosis of any site, pulmonary, disseminated or extrapulmonary
- Mycobacterium, other species or unidentified species, disseminated or extrapulmonary
- Pneumocystis jirovecii pneumonia
- Pneumonia, recurrent
- Progressive multifocal leukoencephalopathy
- Salmonella septicaemia, recurrent
- Toxoplasmosis of brain, onset at age >1 month
- Wasting syndrome attributed to HIV.

Reference

CDC. Revised Surveillance Case Definition for HIV Infection – United States, 2014. MMWR 2014; 63 (RR-03);1-10.

10.5. Appendix 5: Definition of and Procedures for Recording, Evaluating, Follow-Up and Reporting of Adverse Events

10.5.1. Definition of Adverse Events

Adverse Event Definition:

- An AE is any untoward medical occurrence in a patient or clinical investigation participant, temporally associated with the use of a medicinal product, whether or not considered related to the medicinal product.
- NOTE: An AE can therefore be any unfavorable and unintended sign (including an abnormal laboratory finding), symptom, or disease (new or exacerbated) temporally associated with the use of a medicinal product.

Events meeting AE definition include:

- Any abnormal laboratory test results (hematology, clinical chemistry, or urinalysis) or other safety assessments (e.g., ECGs, radiological scans, vital signs measurements), including those that worsen from baseline, and felt to be clinically significant in the medical and scientific judgement of the investigator.
- Exacerbation of a chronic or intermittent pre-existing condition including either an increase in frequency and/or intensity of the condition.
- New conditions detected or diagnosed after study treatment administration even though it may have been present prior to the start of the study.
- Signs, symptoms, or the clinical sequelae of a suspected interaction.
- Signs, symptoms, or the clinical sequelae of a suspected overdose of either study treatment or a concomitant medication (overdose per se will not be reported as an AE/SAE unless this is an intentional overdose taken with possible suicidal/self-harming intent. This should be reported regardless of sequelae).
- "Lack of efficacy" or "failure of expected pharmacological action" per se will not be reported as an AE or SAE. However, the signs and symptoms and/or clinical sequelae resulting from lack of efficacy will be reported if they fulfil the definition of an AE or SAE.

Events NOT meeting definition of an AE include:

- Any clinically significant abnormal laboratory findings or other abnormal safety assessments which are associated with the underlying disease, unless judged by the investigator to be more severe than expected for the participant's condition.
- The disease/disorder being studied or expected progression, signs, or symptoms of the disease/disorder being studied, unless more severe than expected for the

participant's condition.

- Medical or surgical procedure (e.g., endoscopy, appendectomy): the condition that leads to the procedure is an AE.
- Situations where an untoward medical occurrence did not occur (social and/or convenience admission to a hospital).
- Anticipated day-to-day fluctuations of pre-existing disease(s) or condition(s) present or detected at the start of the study that do not worsen.

10.5.2. Definition of Serious Adverse Events

If an event is not an AE per definition above, then it cannot be an SAE even if serious conditions are met (e.g., hospitalization for signs/symptoms of the disease under study, death due to progression of disease, etc.).

Serious Adverse Event (SAE) is defined as any untoward medical occurrence that, at any dose:

Results in death

Is life-threatening

NOTE:

The term 'life-threatening' in the definition of 'serious' refers to an event in which the participant was at risk of death at the time of the event. It does not refer to an event, which hypothetically might have caused death, if it were more severe.

Requires hospitalization or prolongation of existing hospitalization

NOTE:

- In general, hospitalization signifies that the participant has been detained (usually involving at least an overnight stay) at the hospital or emergency ward for observation and/or treatment that would not have been appropriate in the physician's office or out-patient setting. Complications that occur during hospitalization are AEs. If a complication prolongs hospitalization or fulfills any other serious criteria, the event is serious. When in doubt as to whether "hospitalization" occurred or was necessary, the AE should be considered serious.
- Hospitalization for elective treatment of a pre-existing condition that did not worsen from baseline is not considered an AE.

Results in disability/incapacity

NOTE:

- The term disability means a substantial disruption of a person's ability to conduct normal life functions.

 This definition is not intended to include experiences of relatively minor medical significance such as uncomplicated headache, nausea, vomiting, diarrhea, influenza, and accidental trauma (e.g. sprained ankle) which may interfere or prevent everyday life functions but do not constitute a substantial disruption

Is a congenital anomaly/birth defect


Other situations:
 
 Medical or scientific judgment should be exercised in deciding whether reporting is appropriate in other situations, such as important medical events that may not be immediately life-threatening or result in death or hospitalization but may jeopardize the participant or may require medical or surgical intervention to prevent one of the other outcomes listed in the above definition. These should also be considered serious. Examples of such events are invasive or malignant cancers, intensive treatment in an emergency room or at home for allergic bronchospasm, blood dyscrasias or convulsions that do not result in hospitalization, or development of drug dependency or drug abuse

Is associated with liver injury and impaired liver function defined as:
 
 ALT \geq 3xULN and total bilirubin* \geq 2xULN (>35% direct), or ALT \geq 3xULN and INR** > 1.5. 
* Serum bilirubin fractionation should be performed if testing is available; if unavailable, measure urinary bilirubin via dipstick. If fractionation is unavailable and ALT \geq 3xULN and total bilirubin \geq 2xULN, then the event is still to be reported as an SAE.
 
** INR testing not required per protocol and the threshold value does not apply to participants receiving anticoagulants. If INR measurement is obtained, the value is to be recorded on the SAE form.

10.5.3. Definition of Cardiovascular Events

Cardiovascular Events (CV) Definition:

Investigators will be required to fill out the specific CV event page of the eCRF for the following AEs and SAEs:
 
 Myocardial infarction/unstable angina Congestive heart failure Arrhythmias Valvulopathy Pulmonary hypertension

- Cerebrovascular events/stroke and transient ischemic attack
- Peripheral arterial thromboembolism
- Deep venous thrombosis/pulmonary embolism
- Revascularization

10.5.4. Recording of AEs and SAEs

AEs and SAE Recording:

- When an AE/SAE occurs, it is the responsibility of the investigator to review all documentation (e.g., hospital progress notes, laboratory, and diagnostics reports) relative to the event.
- The investigator will then record all relevant information regarding an AE/SAE in the eCRF
- It is **not** acceptable for the investigator to send photocopies of the participant's medical records to GSK in lieu of completion of the GSK, AE/SAE CRF page.
- There may be instances when copies of medical records for certain cases are requested by GSK. In this instance, all participant identifiers, with the exception of the participant number, will be blinded on the copies of the medical records prior to submission to GSK.
- The investigator will attempt to establish a diagnosis of the event based on signs, symptoms, and/or other clinical information. In such cases, the diagnosis will be documented as the AE/SAE and not the individual signs/symptoms.

10.5.5. Evaluating AEs and SAEs

Assessment of Intensity

The investigator will make an assessment of intensity for each AE and SAE reported during the study and will assign it to one of the following categories:

- **Mild:** An event that is easily tolerated by the participant, causing minimal discomfort and not interfering with everyday activities.
- **Moderate:** An event that is sufficiently discomforting to interfere with normal everyday activities
- **Severe:** An event that prevents normal everyday activities. - an AE that is assessed as severe will not be confused with an SAE. Severity is a category utilized for rating the intensity of an event; and both AEs and SAEs can be assessed as severe.
- An event is defined as 'serious' when it meets at least one of the pre-defined outcomes as described in the definition of an SAE.

Assessment of Causality

- The investigator is obligated to assess the relationship between study treatment and the occurrence of each AE/SAE.
- A "reasonable possibility" is meant to convey that there are facts/evidence or arguments to suggest a causal relationship, rather than a relationship cannot be ruled out.
- The investigator will use clinical judgment to determine the relationship.
- Alternative causes, such as natural history of the underlying diseases, concomitant therapy, other risk factors, and the temporal relationship of the event to the study treatment will be considered and investigated.
- The investigator will also consult the Investigator Brochure (IB) and/or Product Information, for marketed products, in the determination of his/her assessment.
- For each AE/SAE the investigator **must** document in the medical notes that he/she has reviewed the AE/SAE and has provided an assessment of causality.
- There may be situations when an SAE has occurred and the investigator has minimal information to include in the initial report to GSK. However, **it is very important that the investigator always make an assessment of causality for every event prior to the initial transmission of the SAE data to GSK.**
- The investigator may change his/her opinion of causality in light of follow-up information, amending the SAE data collection tool accordingly.
- The causality assessment is one of the criteria used when determining regulatory reporting requirements.

Follow-up of AEs and SAEs

- The investigator is obligated to perform or arrange for the conduct of supplemental measurements and/or evaluations as may be indicated or as requested by GSK to elucidate as fully as possible the nature and/or causality of the AE or SAE.
- The investigator is obligated to assist. This may include additional laboratory tests or investigations, histopathological examinations or consultation with other health care professionals.
- If a participant dies during participation in the study or during a recognized follow-up period, the investigator will provide GSK with a copy of any post-mortem findings, including histopathology.
- New or updated information will be recorded in the originally completed CRF.
- The investigator will submit any updated SAE data to GSK within the designated reporting time frames.

10.5.6. Reporting of SAEs to GSK

SAE reporting to GSK via electronic data collection tool

- Primary mechanism for reporting SAEs to GSK will be the electronic data collection tool
- If the electronic system is unavailable for greater than 24 hours, the site will use the paper SAE data collection tool and fax it to the Medical Monitor.
- Site will enter the serious adverse event data into the electronic system as soon as it becomes available.
- The investigator will be required to confirm review of the SAE causality by ticking the 'reviewed' box at the bottom of the eCRF page within 72 hours of submission of the SAE.
- After the study is completed at a given site, the electronic data collection tool (e.g., InForm system) will be taken off-line to prevent the entry of new data or changes to existing data
- If a site receives a report of a new SAE from a study participant or receives updated data on a previously reported SAE after the electronic data collection tool has been taken off-line, the site can report this information on a paper SAE form or to the Medical Monitor by telephone.
- Contacts for SAE receipt can be found at the beginning of this protocol on the Sponsor/Medical Monitor Contact Information page.

SAE reporting to GSK via paper CRF

- Facsimile transmission of the SAE paper CRF is the preferred method to transmit this information to the Medical Monitor or the SAE coordinator
- In rare circumstances and in the absence of facsimile equipment, notification by telephone is acceptable, with a copy of the SAE data collection tool sent by overnight mail
- Initial notification via the telephone does not replace the need for the investigator to complete and sign the SAE CRF pages within the designated reporting time frames.
- Contacts for SAE receipt can be found at this beginning of the protocol on the Sponsor/Medical Monitor Contact Information page.

10.6. Appendix 6: Toxicity Management

10.6.1. Treatment Interruption Due to an Adverse Event

IP may be interrupted at the discretion of the Investigator and according to the severity of the AE. If one or more antiretroviral medications is held due to toxicity or adverse events, all antiretroviral medications must be held to reduce the risk of development of resistance taking into account both the length of the planned interruption and the pharmacokinetic half-life of each antiretroviral of the regimen, in a way to minimize the risk of development of resistance.

No toxicity-related dose reductions of IP will be allowed. IP should be restarted as soon as medically appropriate; in general, for oral dosing, this should be no longer than 14 days after discontinuation (unless Grade 3 or 4 toxicities persist). Any interruption in therapy during the Maintenance Phase, oral dosing, of greater than 7 consecutive days must be discussed with and agreed by the Medical Monitor prior to resumption of therapy. The Medical Monitor must be contacted upon becoming aware of resumption in therapy, if therapy was resumed without prior approval. **IM dosing is expected to occur during the week in which the participant's projected visit falls (as according to the date of the first injection visit [Month 1]). A +0 / -7 day window is stipulated around the projected dosing date for dosing injections at Month 2 and Month 3. A +7 / -7 day window, from the projected visit date, is allowable from the fourth injections forward for IM dosing but not preferred.** Any interruption outside of this guidance MUST be discussed with the Medical Monitor prior to reinitiating IM IP.

Guidance is provided below on general participant management and IP interruptions based on the severity of the AE. All changes in the IP regimen must be accurately recorded in the participant's eCRF.

10.6.2. Liver Chemistry Stopping and Follow-up Criteria

Liver chemistry threshold stopping criteria have been designed to assure participant safety and to evaluate liver event etiology during administration of study drug and the follow-up phase (See also Section 10.3, [Appendix 3](#)). All Phase 3 participants who meet liver stopping criteria will be adjudicated by the ViiV Safety and Labelling Committee (VSLC) – resulting in a case summary, adjudication, and management plan. The VSLC contains an external expert hepatologist, familiar with both DILI and cabotegravir, who will participate in this review. This committee meets on a 3-weekly basis, and can be convened on an ad hoc basis as needed.

Drug Restart Following Transient Resolving Liver Events Not Related to Study Drug

Approval by VSLC for drug restart can be considered where:

Liver chemistries have a clear underlying cause (e.g., biliary obstruction, hypotension, and liver chemistries have improved to normal or are within $1.5 \times$ baseline and $ALT < 3 \times ULN$). Ethics Committee or IRB approval of drug restart must be obtained, as required.

If restart of drug is approved by VSLC in writing, the participant must be provided with a clear description of the possible benefits and risks of drug administration, including the possibility of recurrent, more severe liver injury or death.

The participant must also provide signed informed consent specifically for the restart. Documentation of informed consent must be recorded in the study chart.

Study drug must be administered at the dose specified by VSLC.

Participants approved by VSLC for restarting study drug must return to the clinic once a week for liver chemistry tests for a minimum of one month and thereafter for as long as clinically indicated and then laboratory monitoring may resume as per protocol. If protocol defined stopping criteria for liver chemistry elevations are met, study drug must be stopped.

Refer to Section 10.2, Appendix 2, U.S. Department of Health and Human Services, National Institutes of Health, National Institute of Allergy and Infectious Diseases, Division of AIDS. Division of AIDS (DAIDS) Table for Grading the Severity of Adult and Pediatric Adverse Events, Version 2.1. [March 2017]. Available from: <https://rsc.tech-res.com/docs/default-source/safety/daids-ae-grading-table-mar2017.pdf>

Refer to Section 10.3.3: Liver Safety – Study Treatment Restart Guidelines for further details.

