Drug Induced Liver Injury (DILI)	
A small proportion of participants in the CAB program to date (total exposure >3100 participants) have developed transaminitis (elevated liver transaminases characterised by predominant alanine aminotransferase (ALT) elevation). In most participants, transient transaminitis was explained by acute hepatitis C infection (majority) and other systemic infections. In a small number of participants, there was not an alternative explanation, suggesting a mild form of drug induced liver injury (DILI) without hepatic dysfunction, which resolved upon withdrawal of treatment with CAB.
 
All participants with suspected DILI identified to date were receiving oral CAB.
	
 Exclusion criteria as described in Section 5.2 will prohibit participation of PLWHIV who have significant liver impairment based on screening liver chemistry including transaminases (ALT and Aspartate aminotransferase [AST]) as well on prior medical history. Participants with a history of chronic liver disease with ongoing inflammation and/or fibrosis will have additional confirmatory assessments to confirm suitability for entry into the study. Liver transaminases (ALT and AST) will be monitored throughout this study (refer to Schedule of Activities Table, Section 1.5) and the liver chemistry stopping criteria will be adopted as described in Section 10.6.2 of this protocol. Participants will be withdrawn from CAB treatment where no compelling alternative cause is identified, and DILI is suspected. Participants who develop ALT ≥ 3 times the upper limit of normal (ULN) while on study must consult with Medical Monitor prior to initiation or continuation of CAB LA + RPV LA.

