- Participant requires substitution or dose reduction of CAB LA, RPV LA (oral bridging supply and potential for a second loading dose may be permissible following discussion with the Medical Monitor)
- Liver toxicity where stopping criteria are met and no compelling alternate cause is identified (see Section 10.6.2);

- Renal toxicity is met and no compelling alternate cause is identified;
- Corrected QT interval (QTc) >550 msec from three or more tracings separated by at least 5 minutes and considered causally related to IP. *Note: ECGs are not routinely conducted in this study.*
- Grade 4 clinical AE considered causally related to study drug;
- Participant has a Grade 3 or higher rash or Grade 2 rash with evidence of systemic involvement and no compelling alternative cause is identified.
- Participant withdrew consent

Safety data for all participants who receive any amount of study drug, including participants who withdraw from the study, will be included in evaluations of safety.

If a participant is prematurely or permanently withdrawn from the study, the procedures described in the Schedule of Activities Table, Section 1.5, for the in-clinic Withdrawal visit are to be performed. An in-clinic Follow-Up visit will be conducted 4 weeks after the last dose of study medication for participants with ongoing AEs, and serious adverse events (SAEs) related & not related to study drug and also any laboratory abnormalities that are considered to be AEs or potentially harmful to the participant, at the last on-study visit.

All data from the Withdrawal visit will be recorded, as they comprise an essential evaluation that should be done prior to discharging any participant from the study.

The following actions must be taken and documented in relation to a participant who fails to attend the clinic for a required study visit:

- a. The site must attempt to contact the participant and re-schedule the missed visit as soon as possible.
- b. The site must counsel the participant on the importance of maintaining the assigned visit schedule and ascertain whether or not the participant wishes to and/or should continue in the study.

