10.6.3. Grade 1 or Grade 2 Toxicity/Adverse Event

Participants who develop a Grade 1 or Grade 2 AE or toxicity may continue IP at the discretion of the Investigator. (NOTE: See Section 10.6 Appendix 6, Specific Toxicities/Adverse Event Management” for exceptions to this guideline). Participants who choose to withdraw from study due to a Grade 1 or 2 AE should have study withdrawal and follow-up evaluations completed.

Participants who develop ALT ≥ 3 times ULN while on study must consult with Medical Monitor prior to initiation or continuation of CAB LA and RPV LA.

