10.6.4. Grade 3 Toxicity/Adverse Event

Participants who develop a Grade 3 AE or toxicity should be managed as follows:

- If the Investigator has compelling evidence that the Grade 3 AE or toxicity has not been caused by IP, dosing may continue after discussion with the Medical Monitor.
- Participants who develop a Grade 3 AE or toxicity, which the Investigator considers related or possibly related to the IP, should have the IP withheld and be rechecked each week until the AE returns to Grade 2. Once the AE is Grade ≤ 2 , IP may be re-started.
- Should the same Grade 3 AE recur within 28 days in the same participant, the IP should be permanently discontinued and the participant withdrawn from study.

- Participants experiencing Grade 3 AEs requiring permanent discontinuation of IP should be followed weekly until resolution of the AE and to have withdrawal study evaluations completed. A follow-up visit should be performed 4 weeks after the last dose of IP. Any participant receiving at least one dose of CAB LA and /or RPV LA who discontinue IP / Withdraw will initiate treatment with HAART and enter the Long-Term Follow-Up Phase for 52 weeks of follow up.
- Participants with Grade 3 asymptomatic laboratory abnormalities should be investigated for all potential non-drug related causes, and, following discussion with the Medical Monitor, may continue IP if the Investigator has compelling evidence that the toxicity is not related to IP, with the exception of liver chemistry stopping criteria (See Section 10.6.2). Isolated Grade 3 lipid abnormalities do not require withdrawal of IP.

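### Section 10.6.2 is cited for the liver stopping criteria but states no stopping threshold, and the rules for resuming drug in 10.6.2, 10.6.4 and Appendix 3 conflict

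*Protocol*

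**What the plan says.** Section 7 lists, among the reasons for which study intervention must be discontinued, "Liver toxicity where stopping criteria are met and no compelling alternate cause is identified (see Section 10.6.2". The drug-induced liver injury (DILI) row of the risk table in Section 2.3.1 says that "the liver chemistry stopping criteria will be adopted as described in Section 10.6.2 of this protocol". Section 10.6.4 lets participants with asymptomatic Grade 3 laboratory abnormalities continue if there is compelling evidence that drug is not the cause, "with the exception of liver chemistry stopping criteria (See Section 10.6.2". Section 10.6.5 makes the same exception for Grade 4 without giving a section number.

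Section 10.6.2 opens with "Liver chemistry threshold stopping criteria have been designed to assure participant safety". It then says "All Phase 3 participants who meet liver stopping criteria will be adjudicated by the ViiV Safety and Labelling Committee (VSLC"), with a case summary and management plan. It sets conditions for restart after liver events not related to drug, requires weekly liver tests after restart, and ends with "If protocol defined stopping criteria for liver chemistry elevations are met, study drug must be stopped". It refers on to the DAIDS grading table and to Section 10.3.3.

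**The concern.** Four sections depend on criteria that the cited section announces but does not state. DILI is the first risk in the protocol's own risk table, and the criteria are part of its stated mitigation. They also decide who goes to the VSLC. Without them, two sites seeing the same liver chemistry could act differently and both believe that they followed the protocol. The sponsor would have no fixed rule for deciding which cases should have been stopped or adjudicated. Appendix 3 itself cites 13% mortality after rechallenge following DILI across all drugs, so which pathway a case enters matters.

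Other mandatory stops in this protocol are numeric: QTc above 550 msec (7.1.1) and two consecutive HIV-1 RNA values of at least 200 c/mL (7.1.3). The liver stop is not.

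**Working it through.** No sample-size or power figure is involved. The check traces each reference and lists what every liver value in the protocol is used for.

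**1. Trace the references.** Sections 2.3.1, 7 and 10.6.4 lead to 10.6.2, and 10.6.5 uses the same term. Section 10.6.2 leads on to the DAIDS table, which only grades, and to 10.3.3, which deals with restart once stopping criteria have already been met. Section 10.3.6 says to discontinue for protocol-defined elevations as the protocol specifies, so the chain returns to its start.

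**2. List the liver values and their stated use.**

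| Place | Value | Use |
|---|---|---|
| 5.2, criterion 22 | ALT ≥5xULN, or ALT ≥3xULN with bilirubin ≥1.5xULN | Eligibility |
| 2.3.1 and 10.6.3 | ALT ≥3xULN | Medical Monitor consultation |
| 10.3.1, 10.3.2, Table 13 | ALT 3xULN, bilirubin 2xULN, INR 1.5 | Rechallenge risk factors |
| 10.3.5 | Bilirubin >2xULN or INR ≥1.5 | Reporting severe reactions after resumption |
| 10.3.3, Table 14 | Within 1.5x baseline and ALT <5xULN | Restart |
| 10.6.2 | Within 1.5x baseline and ALT <3xULN | Restart |
| 10.5.2 | ALT ≥3xULN with bilirubin ≥2xULN or INR >1.5 | SAE definition |

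None is labelled a stopping criterion. Thresholds that stop drug: 0. Sections that depend on them: 4.

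**3. Rule out a lost table or figure.** Tables 13 and 14 belong to Appendix 3 and Table 15 to Appendix 7. Figures 5 and 6 belong to Appendix 3, with captions describing the VSLC rechallenge and restart processes, and Figure 7 belongs to Appendix 8. No number is missing at 10.6.2. The contents list puts 10.6.2 on page 149 and both 10.6.3 and 10.6.4 on page 150, which leaves little room for a dropped item.

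**4. What still operates.** Four provisions work without the missing criteria:
- withdrawal where DILI is suspected and no compelling alternative cause is found (2.3.1), on judgement;
- consultation at ALT ≥3xULN (2.3.1, 10.6.3);
- permanent discontinuation for Grade 2 or higher rash with an ALT increase (10.6.6.10.1);
- the general grade rules, including Grade 4 discontinuation unless compelling evidence shows that drug is not the cause (10.6.5).

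None of them states a liver stopping threshold or refers a case to the VSLC.

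**5. Resuming after a possibly related event.** The DAIDS table puts ALT 5.0 to <10.0xULN at Grade 3. Under 10.6.4 a related or possibly related Grade 3 event is withheld, rechecked weekly, and may resume once Grade 2 or below, which for ALT means below 5.0xULN. That bullet has no liver exception and no VSLC step. Section 10.3.1 says that a case is to be treated as a rechallenge if there is any reasonable likelihood that drug was the cause, and 10.3.2 takes a rechallenge request to the full VSLC. The two texts give different routes for the same event.

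**6. Restart after an unrelated event.** Both versions require normal values or values within 1.5x baseline, then add a different ALT cap. With baseline ALT b in multiples of ULN, a cap c can matter only where 1.5 × b ≥ c, that is b ≥ c/1.5.
- 10.6.2: b ≥ 3/1.5 = 2.0xULN.
- 10.3.3: b ≥ 5/1.5 = 3.33xULN.

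The caps therefore give different answers only for participants with baseline ALT of at least 2.0xULN. Criterion 22 admits some of them, because it excludes on ALT alone only from 5xULN.

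**The case against.** The strongest reply is that a reader might infer more than the text shows.

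- **That nothing triggers a stop.** This is not so. Section 2.3.1 requires withdrawal for suspected DILI without a compelling alternative cause, at any grade, and the rash and Grade 4 rules also stop drug. What is missing is the objective trigger.
- **That restart without the VSLC is permitted.** Appendix 3 can fairly be read as capturing any plausibly drug-related Grade 3 ALT event. But its headings and requests are framed around participants who met stopping criteria, so its own entry point rests on the unstated thresholds. The supported statement is that 10.6.4 and Appendix 3 conflict.
- **That a combined ALT and bilirubin rise in the SAE range is always Grade 2, and so always left to investigator discretion.** The DAIDS table grades direct bilirubin separately. Above ULN with other signs and symptoms of hepatotoxicity it is Grade 3, so some of these cases leave Grade 2.
- **That Section 7 contradicts 10.6.4 and 10.6.5 on alternate causes.** They can be read in sequence: hold when the criteria are met, investigate, then stop for good if no other cause is found.
- **That Section 10.6.2 contains only restart rules.** It also covers adjudication, post-restart monitoring and a post-restart stop. Both the adjudication and that stop still depend on the same unstated criteria.

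These replies narrow the point. None of them supplies a threshold.

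**Conclusion.** The point stands in this form: Section 10.6.2 is cited for liver stopping criteria that neither it nor any other section states. The mandatory liver stop in Section 7, the liver exceptions in 10.6.4 and 10.6.5, and VSLC adjudication therefore lack an objective trigger. Two conflicts about resuming drug come with it: 10.6.4 against 10.3.1 and 10.3.2 on possibly related Grade 3 events, and ALT <3xULN against <5xULN on restart. The second affects only participants with baseline ALT of at least 2.0xULN.

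The conclusion assumes that Figures 5 and 6, which cannot be seen here, hold no stopping threshold (their captions describe committee processes), and that the criteria are not left to the Study Procedures Manual. Section 6.6 describes that manual as holding information not required in the protocol, while 2.3.1 places the criteria in the protocol.

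A reader might also infer a distortion of the secondary endpoint on discontinuation due to adverse events. The documents do not show one. It is a descriptive proportion, no hypothesis test is planned, and no size or direction of effect can be derived.

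**What to change.** State in Section 10.6.2 the sponsor's own liver chemistry stopping criteria, so that the references in 2.3.1, 7, 10.6.4, 10.6.5 and Appendix 3 lead to something that can be applied. Then reconcile Sections 2.3.1, 7, 10.3.1 to 10.3.6 and 10.6.2 to 10.6.5 on two matters: how the general grade rules relate to the liver and VSLC pathway, and which restart condition applies. The content of the criteria, and the choice between conflicting rules, belong to the sponsor; none is proposed here.

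The cost is protocol amendment wording with the usual ethics approval. The VSLC and the scheduled chemistry draws already exist. If the sponsor's criteria use INR, the schedule should be checked, because Table 3 lists it only at Screening and Withdrawal.
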